NCT02848599

ID: 25-1:6563-3/2014

Document Date: May 26, 2017

The Influence of  
Postoperative Analgesia  
on Systemic Inflammatory  
Response and POCD  
After Femoral Fractures  
Surgery

The study was approved by the University Hospital Osijek Ethics Committee (Approval number 25-1:6563-3/2014, 19.5.2014.) and written informed consent was obtained from all subjects. The study design was a prospective, randomized, controlled trial. All patients received spinal anesthesia and one of two techniques of postoperative analgesia: intravenous patient-controlled analgesia (PCA) with morphine or patient-controlled epidural analgesia (PCEA) with 0.125% levobupivacaine. According to technique of postoperative analgesia which was applied, patients were allocated into two groups, the morphine group and the levobupivacaine group. Randomization was done before surgery by pulling out the envelope in which it was written the group division. Inclusion criteria were age  $\geq$  65, American Society of Anesthesiologists (ASA) physical status I-III, Mini-Mental State Examination (MMSE) score  $\geq$  17. Exclusion criteria were age  $<$  65, ASA physical status > III, MMSE score  $<$  17, history of dementia, schizophrenia, Parkinson's disease and cerebrovascular disease, use of opioids and benzodiazepines longer than one month before surgery, alcoholism, severe liver disease (class C according to Child-Pugh classification), severe kidney disease requiring hemodialysis, multiple trauma and the presence of head injury, communication issues such as serious hearing or visual impairment, any contraindication for regional anesthesia and for the both techniques of postoperative analgesia. Cefazolin 1g was given to all patients 30 minutes before incision and two other doses were given postoperatively. All patients were sedated with midazolam, 2 to 3 mg intravenously, before induction of anesthesia. In the morphine group spinal anesthesia was induced with subarachnoidally injection of 12.5-15 mg 0.5% levobupivacaine. In the levobupivacaine group combined spinal-epidural anesthesia was performed. First, the epidural space was entered with Tuohy epidural needle and the spinal needle was introduced via the lumen of the epidural needle into the subarachnoid space through which 12.5-15 mg of 0.5% levobupivacaine was injected. After that epidural catheter was inserted in the epidural space and its position was checked radiologically and confirmed with the test dose of 0.5% levobupivacaine after the spinal anesthesia was released. During the operation blood pressure was measured non-invasively every 5 minutes and its decrease greater than 20% from preoperative values was corrected by fluid administration and incremental IV injections of vasoconstrictors. The ECG and peripheral oxygen saturation by pulse oximeter were continuously monitored. Postoperative analgesia was obtained using patient-controlled analgesia (PCA) for the first 72 h. In the morphine group intravenous PCA was provided with the following settings: 0.5-2 mg/h basal flow, 0.5 mg bolus dose, and a 20-min lockout. Postoperative epidural PCA analgesia was obtained with 0.125% levobupivacaine with 6-12 ml/h basal flow, 2 ml bolus dose, and a 20-min lockout. Analgesia was assessed by Numerical Rating Scale (NRS), from 0 (no pain) to 10 (maximum pain) every three hours 72h postoperatively and then 3 times a day until discharge. In all patients complete blood count, differential blood count, CRP and fibrinogen were calculated 30 min before induction of anesthesia, 24h, 72h and 120h postoperatively. Blood glucose level was measured every 4 hours for 72h after

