
surgery and further depending on the values. The plasma concentrations of IL-6 was measured 30 min before induction of anesthesia, 24h and 72h postoperatively. Duration of surgery, blood loss, erythrocyte transfusion, body temperature and postoperative hospital stay were recorded. Cognitive functions were assessed using Mini-Mental State Examination (MMSE) preoperatively (baseline) and from the 1st to the 5th postoperative day and on the day of discharge (the day of surgery was marked as 0 day), once a day between 6 and 8 am. Anxiety and depression were assessed using Hospital Anxiety and Depression Scale (HADS) preoperatively (baseline) and on the 1st and 5th postoperative day and on the day of discharge once a day, at the same time when cognitive functions were evaluated.

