NCT02848599

ID: 25-1:6563-3/2014

The Influence of
Postoperative Analgesia
on Systemic Inflammatory
Response and POCD
After Femoral Fractures
Surgery

Document Date: May 26, 2017

Category data were represented by absolute and relative frequencies. Variations of category variables were tested by Fisher's exact test. The numerical data are described by the median and the limits of the interquartile range. The normality of distribution of observed numeric variables was tested by the Shapiro -Wilk test. The differences between the normal distribution of numeric variables between the two independent groups were tested by Mann-Whitney's In Test. To determine the difference between the two dependent samples, Friedman's test was used. Logistic regression was used to assess the influence of several factors on the likelihood that POCD would develop in the observed subjects. The receiver operating curve (ROC) analysis was used to determine the optimal threshold, area under the curve (AUC), specificity, and sensitivity of the tested parameters. All P values were two-tailed. The level of significance was set at Alpha = 0.05. The statistical analysis was performed using MedCalc Statistical Software version 14.12.0 (MedCalc Software bvba, Ostend, Belgium; <http://www.medcalc.org>; 2014)

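### The SAP chooses the ROC cut-off and reports its sensitivity and specificity from one unvalidated analysis, so on average both will be too high, mainly sensitivity

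*SAP*

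**What the plan says.** The SAP is a single paragraph. Its ROC sentence says that ROC "analysis was used to determine the optimal threshold, area under the curve (AUC), specificity, and sensitivity of the tested parameters". It does not name the outcome. POCD is inferred from the sentence before it: "Logistic regression was used to assess the influence of several factors on the likelihood that POCD would develop in the observed subjects".

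The parameters are not listed. The protocol offers several plausible ones: "complete blood count, differential blood count, CRP and fibrinogen were calculated 30 min before induction of anesthesia, 24h, 72h and 120h postoperatively", and "The plasma concentrations of IL-6 was measured 30 min before induction of anesthesia, 24h and 72h postoperatively".

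The only data source is the trial itself: "The study design was a prospective, randomized, controlled trial". Neither document gives a pre-set cut-off, a rule for what counts as optimal, a split sample, cross-validation, a bootstrap correction or a second cohort. Neither states a sample size or an expected POCD rate.

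**The concern.** A cut-off chosen because it performs best in a sample fits the chance features of that sample as well as the real signal. Sensitivity and specificity read off at that cut-off, in the same patients, carry the chance part with them. A published cut-off would then seem to separate patients with and without POCD better than it would in the next series of patients. A weak marker would look moderately useful, and a marker unrelated to POCD would show an apparent J above zero.

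What is at stake is the credibility of any cut-off for predicting POCD. The comparison of the two analgesia techniques is not involved.

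**Working it through.** **Inputs.** The plan states no figure that could be reproduced. From the documents: one trial, one ROC analysis, cut-off and accuracy both taken from it. Assumed, because the documents are silent: 60, 80 or 120 patients; POCD in 20% or 30% (from 60 × 0.20 = 12 to 120 × 0.30 = 36 cases); a normally distributed marker with equal spread in cases and non-cases; direction fixed in advance; the Youden cut.

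**Direction of the bias.** Write apparent sensitivity at cut c as S(c) + X(c), where S(c) is the true value and X(c) the sampling error, with mean zero at any fixed c. Hold the non-cases fixed and let f(c) = S(c) + apparent specificity at c, with maximiser c0. The chosen cut c* maximises f(c) + X(c), so

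X(c*) ≥ X(c0) + [f(c0) − f(c*)] ≥ X(c0).

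c0 does not depend on the cases, so X(c0) has mean zero and the mean of X(c*) is at least zero. The same argument with the roles exchanged covers specificity. It applies to the Youden rule and to any weighted sum of the two measures.

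**Size, one marker.** In simulation (20,000 replicates per scenario), apparent values were compared with the true values at the same chosen cut:

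| Marker | Measure | Apparent | True at chosen cut |
|---|---|---|---|
| AUC 0.70 | Sensitivity | 0.69-0.75 | 0.61-0.62 |
| AUC 0.70 | Specificity | 0.66-0.68 | 0.64-0.65 |
| AUC 0.70 | J | 0.36-0.42 | 0.26-0.27 |
| No information | J | 0.12-0.18 | 0 |

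Sensitivity is too high by about 0.69 − 0.62 = 0.07 to 0.75 − 0.62 = 0.13. Specificity is too high by about 0.66 − 0.64 = 0.02 to 0.68 − 0.64 = 0.04. J is too high by about 0.36 − 0.27 = 0.09 to 0.42 − 0.26 = 0.16. Mean AUC was 0.70 and 0.50, so AUC is not biased here.

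**Dependence on the assumptions.** A separate, wider simulation (3,000 replicates; AUC 0.70, Youden cut) gave these excesses in percentage points. The J column is the sum of the two before it:

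| N | POCD | Cases | Sensitivity | Specificity | J |
|---|---|---|---|---|---|
| 60 | 15% | 9 | +15.5 | +2.8 | +18.3 |
| 60 | 30% | 18 | +9.7 | +4.1 | +13.8 |
| 60 | 50% | 30 | +6.2 | +6.0 | +12.2 |
| 100 | 30% | 30 | +7.2 | +3.0 | +10.2 |
| 200 | 30% | 60 | +4.7 | +2.1 | +6.8 |

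Across all 36 Youden scenarios (N 40-200, POCD 15-50%, AUC 0.6-0.8) both biases were positive: sensitivity +2.6 to +19.9 points, specificity +1.1 to +8.1. At N = 60 they also stayed positive under three other rules: closest to the corner, maximum accuracy, and best specificity with sensitivity of at least 90%.

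**Does the fix work?** Ten-fold cross-validation repeated 10 times, with the cut re-selected in each training set (1,000 replicates), gave mean J −0.01 to 0.01 for a marker with no information and 0.25-0.28 for AUC 0.70, against a true 0.26-0.27. Bootstrap optimism correction left 35-41% of the inflation. Nominal 95% Wilson intervals placed on the cross-validated values covered only 71-87% for sensitivity and 60-83% for specificity.

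**The case against.** The strongest reply is that this is a routine, ancillary ROC analysis in a completed study, so the point is a reporting caveat. The size is also assumed throughout: with 200 patients and 30% POCD the excess is only 4.7 and 2.1 points. AUC is reported in the same sentence and is unbiased for a single marker with fixed direction, so a marker with no information would average 0.50 and give itself away. Much of this stands. It limits the weight of the point and argues for a simple remedy. It does not remove the bias, because the SAP neither calls the cut-offs exploratory nor warns that their accuracy is optimistic.

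A reader might infer something stronger: that many markers and times were screened and only the best reported, which would inflate the figures further and inflate AUC too. The documents do not support that. The ROC sentence promises results for the tested parameters in the plural, and nothing says that some are withheld or that direction is chosen from the data. Any count of candidates would also be arbitrary, since the SAP does not list them and the protocol measures blood counts as well as CRP, fibrinogen and IL-6.

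A reader might also want a bootstrap of the whole cross-validation to give intervals. With 12 POCD cases, a resample holds on average 12 × [1 − (11/12)^12] = 7.8 distinct cases, and about 95% of resamples have fewer than 10. If copies of a patient stay in one fold, some of 10 test folds then contain no case. That is not a sound requirement here.

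**Conclusion.** The concern holds. On average, sensitivity and specificity at the chosen cut-off will be higher than that cut-off would achieve in new patients from the same population. In one data set either could still fall low. That the same patients set and test the cut-off is an inference, but no other data source is named.

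For 60-120 patients, POCD in 20-30%, a Youden cut and true AUC 0.70, the excess is about 7-13 points in sensitivity and 2-4 in specificity. Sensitivity suffers more because cases are assumed to be the minority; at 50% POCD the two are about equal. None of these inputs is in the documents, so the direction is firm and the size is conditional. If marker or direction was chosen from the data the inflation is larger, but the SAP does not say whether it was.

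This should be corrected in the SAP and in reporting. It gives no ground to doubt the randomised comparison, or the AUC of a single marker with direction fixed in advance.

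**What to change.** Add to the SAP:

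> For each parameter tested, sensitivity and specificity at the cut-off are estimated by repeated stratified cross-validation (number of folds no larger than the number of POCD cases) that re-selects the cut-off, and the direction or marker if chosen from the data, in each training set. All tested parameters, sampling times and the threshold rule are reported, AUC is given with a 95% CI, and cut-offs are labelled exploratory.

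The limit on folds ensures that stratification can place at least one POCD case in every test fold. Simple binomial intervals should not be attached to the cross-validated figures, because they ignore the selection of the cut-off and cover too little.

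If cross-validation is not done, the minimum is a sentence stating that sensitivity and specificity come from the data that set the cut-off and are optimistic.

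The cost is a short re-analysis of existing data, possibly outside the named package ("The statistical analysis was performed using MedCalc Statistical Software version 14.12.0"). The accuracy figures will be less favourable. They will also be noisy: under the assumptions above, the SD of the cross-validated J for one marker is about 0.10-0.18, and the report should say so.
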